12.2. Determination of Sample Size

Sample size estimation was performed on both pharmacodynamic endpoints.

Using a 2-sided Type I error rate at $\alpha=0.05$ and assuming a mean difference in $E_{max_urge(\text{controlled})}$ between own-brand cigarette and nicotine polacrilex gum of 15.85 points and standard deviation (SD) of 28.44, 54 completed subjects will be required to detect a significant difference between own-brand cigarette and nicotine polacrilex gum with greater than 80% power.

Using a 2-sided Type I error rate at $\alpha=0.05$ and assuming a mean difference in $E_{max_plst(\text{controlled})}$ between own-brand cigarette and nicotine polacrilex gum of 35.21 points and SD of 31.82, estimate based on data obtained from the study site, 16 completed subjects will be adequate to detect a significant difference between own-brand cigarette and nicotine polacrilex gum with greater than 80% power.

An appropriate number of subjects will be randomized on Day 1 (Part A) to ensure that a minimum of 54 subjects complete the study. Replacement subjects may be enrolled to ensure that the minimum number of subjects complete the study.

12.3. Analysis Populations

The study analysis populations will consist of

- **Randomized Population (Part A):** All subjects who are randomized into Part A.
- **Randomized Population (Part B):** All subjects who are randomized into Part B.
- **Safety Population:** All randomized subjects who use at least one of the study products. This will include Day -1 (Check-In and product trial) and study days after the randomization. The Safety Population will be used for the summary of subject demographics, baseline characteristics, safety information and AEs.
- **Pharmacodynamic Population:** All subjects who use any study product and have pre-use (Tobacco/Nicotine Withdrawal questionnaire) and at least one post-use (for Tobacco/Nicotine Withdrawal and Direct Effects of Product) VAS score for the Controlled Use Session of Part B. This population will be used for statistical analyses of the pharmacodynamic measures.

- **Pharmacokinetic Population:** All subjects who use any study product and have pre- and at least one post-use plasma concentration value for the Controlled Use Session of Part B. The PK Population will be used for statistical analyses of the PK parameters.
- **Completer Population:** All randomized subjects who complete all product use sessions and have pharmacodynamic and PK data in the Controlled Use Session of Part B. This dataset will be used for analyses of the two primary pharmacodynamic endpoints as a sensitivity analyses to the primary analyses.

12.4. Planned Analyses

12.4.1. Subject Disposition

Disposition of each analysis population will be summarized using descriptive statistics. Data from subjects who discontinue from the study will also be summarized by last product used and reason for discontinuation.

12.4.2. Demographics and Other Baseline Characteristics

Descriptive statistics will be reported for continuous demographic variables (age, weight, height, and BMI) and frequency counts will be tabulated for categorical demographics variables (gender, ethnicity, and race). In addition, number of cigarettes smoked per day, as well as the duration of tobacco use (derived as the interval between tobacco use start date and the ICF signature date), will be summarized by descriptive statistics. Responses for smoking history and number of tobacco products used per day will be listed in the substance usage listing.

12.4.3. Analysis of Pharmacodynamic Measures

12.4.3.1. Part A

Responses to Use the Product Again VAS will be summarized by study product using descriptive statistics (n, mean, SD, median, Q1, Q3, min, max). A summary table of frequencies may also be provided.

Descriptive statistics (n, mean, SD, median, Q1, Q3, min, max) will be provided for amount of product used by product (number of cigarettes for own-brand and VLN cigarettes, and number of nicotine gum pieces), duration of time used (time spent per cigarette and duration of gum in mouth), and number of inhalations (puffs) per cigarette for own-brand and VLN cigarettes.

12.4.3.2. Part B

Responses to each Tobacco/Nicotine Withdrawal Questionnaire and Direct Effects of Product Questionnaire item will be summarized by time point for each study product, and product use condition. For Tobacco/Nicotine Withdrawal VAS scores, descriptive statistics (n, mean, SD, median, Q1, Q3, min, max) for the difference from pre-use at each time point will also be reported. Derived parameters (E_{max}) for each questionnaire item will be summarized using descriptive statistics.

A linear mixed effects model for analysis of variance/covariance (Proc Mixed) will be performed on $E_{max_urge(controlled)}$ and $E_{max_plst(controlled)}$. The model will include E_{max} as the response variable, sequence, study product, and period as fixed model effects, baseline score as a covariate (for E_{max_urge} only), and subject nested-within sequence as a random effect. Sequence will be tested using subject nested-within-sequence as the error term. Least square mean (LSM) and 95% confidence interval (CI) for each Study Product group will be provided. Comparisons will be made for Product A vs. B, A vs. C and B vs. C. The comparison between Product A and Product C will be used as a comparison for internal validity. The LSM difference, p-value and 95% CI of the difference will be provided.

The same model will be used for $E_{max_urge(uncontrolled)}$ and $E_{max_plst(uncontrolled)}$, and all E_{max} of other questions in the Tobacco/Nicotine Withdrawal Questionnaire and Direct Effects of Product Questionnaire for the controlled and uncontrolled product uses in Part B. Responses to Use the Product Again VAS will be summarized by study product using descriptive statistics (n, mean, SD, median, Q1, Q3, min, max). A summary table of frequencies may also be provided.

Descriptive statistics (n, mean, SD, median, Q1, Q3, min, max) will be provided on duration of time a product is used (time spent per cigarette and duration of gum in mouth), number of inhalations (puffs), and duration of inhalation (per puff) per cigarette for own-brand and VLN cigarettes.

12.4.3.3. Adjustment for Covariates

Baseline (pre-use) score will be included as a covariate for all pharmacodynamics measures for which a pre-use score is collected.

12.4.3.4. Handling of Dropouts or Missing Data

Missing pharmacodynamic data, including reasons for the missing data, will be listed by subject and examined on a case-by-case basis to determine if these affect subject allocation. No imputation of missing pharmacodynamic data will be performed.

12.4.3.5. Interim Analyses and Data Monitoring

No interim analyses will be performed.

12.4.3.6. Multiple Comparison/Multiplicity

Multiple comparison adjustments will not be made.

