5.2. Study Rationale

The purpose of the current study is to provide an abuse liability assessment of VLN cigarettes compared with own-brand cigarettes and nicotine polacrilex gum in current manufactured filtered king size cigarette smokers, as recommended in "FDA Draft Guidance for Industry

Modified Risk Tobacco Products ([March 2012](#))”. Results of this study may provide supporting evidence for lower abuse liability of VLN cigarettes relative to own-brand cigarettes.

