6. STUDY OBJECTIVES

6.1. Primary Objective

The primary objective of the study is:

- To evaluate the abuse liability of VLN cigarettes (0.4 mg nicotine/gram of tobacco) relative to own-brand cigarettes and nicotine polacrilex gum under controlled use and uncontrolled use conditions.

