#### PD Parameters

The following subjective effect parameters will be calculated for each subject and treatment:

Questionnaire	PD Parameter	Definition
Tobacco/Nicotine Withdrawal Questionnaire	$E_{max\_item(controlled)}$	The maximum reduction in VAS score for each item during the first product use in Part B
	$E_{max\_item(uncontrolled)}$	The maximum reduction in VAS score for each item during the second product use in Part B
Direct Effects of Product Questionnaire	$E_{max\_item(controlled)}$	The largest VAS score recorded for the response to each item during the first product use in Part B
	$E_{max\_item(uncontrolled)}$	The largest VAS score recorded for the response to each item during the second product use in Part B

The definition of the different item in each questionnaire is detailed in the table below.

Questionnaire	Item	Question
Tobacco/Nicotine Withdrawal Questionnaire	$E_{max\_urge(controlled)}$ $E_{max\_urge(uncontrolled)}$	Urge to smoke
	$E_{max\_anx(controlled)}$ $E_{max\_anx(uncontrolled)}$	Anxious
	$E_{max\_diffct(controlled)}$ $E_{max\_diffct(uncontrolled)}$	Difficulty Concentrating
	$E_{max\_impat(controlled)}$ $E_{max\_impat(uncontrolled)}$	Impatient
	$E_{max\_crav(controlled)}$ $E_{max\_crav(uncontrolled)}$	Craving a Cigarette

Direct Effect of Product	$E_{max\_plst}(\text{controlled})$	Is the product "Pleasant" right now?
	$E_{max\_plst}(\text{uncontrolled})$	
	$E_{max\_stf}(\text{controlled})$	Is the product "Satisfying" right now?
	$E_{max\_stf}(\text{uncontrolled})$	
	$E_{max\_calm}(\text{controlled})$	Is the product making you feel "Calm" right now?
	$E_{max\_calm}(\text{uncontrolled})$	
	$E_{max\_conc}(\text{controlled})$	Is the product helping you "Concentrate" right now?
	$E_{max\_conc}(\text{uncontrolled})$	
	$E_{max\_awake}(\text{controlled})$	Is the product making you feel more "Awake" right now?
	$E_{max\_awake}(\text{uncontrolled})$	
	$E_{max\_sick}(\text{controlled})$	Is the product making you feel "Sick" right now?
	$E_{max\_sick}(\text{uncontrolled})$	
	$E_{max\_hunger}(\text{controlled})$	Is the product reducing your "Hunger" for food right now?
	$E_{max\_hunger}(\text{uncontrolled})$	
	$E_{max\_more}(\text{controlled})$	Would you like "More" of the product right now?
	$E_{max\_more}(\text{uncontrolled})$	

The items  $E_{max\_urge}(\text{controlled})$  and  $E_{max\_plst}(\text{controlled})$  will be the primary endpoints of the study while the remaining items will be secondary endpoints.

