## Statistical Analysis of Subjective Effect Parameters

A linear mixed effects model for analysis of variance/covariance (Proc Mixed) will be performed on  $E_{max\_urge}(\text{controlled})$  and  $E_{max\_plst}(\text{controlled})$ . The model will include  $E_{max}$  as the response variable, sequence, study product, and period as fixed model effects, baseline score as a covariate, and subject nested-within sequence as a random effect. Sequence will be tested using subject nested-within-sequence as the error term. Least square mean (LSM) and 95% confidence interval (CI) for each study product group will be provided. Comparisons will be made for Product A vs. B, A vs. C and B vs. C. The comparison between Product A and Product C will be used as a comparison for internal validity. The LSM difference, p-value and 95% CI of the difference will be provided.

The SAS code for the statistical modeling is:

```
Proc MIXED data=test;
  class subject sequence period product;
  model Emax = sequence period product baseline / ddfm=KR;
  random subject (sequence) / type=UN;
  estimate "Product A vs Product B" product 1 0 -1 /cl alpha=0.05;
  estimate "Product A vs Product C" product 1 0 -1 /cl alpha=0.05;
  estimate "Product B vs Product C" product 0 1 -1 /cl alpha=0.05;
  lsmeans product/cl alpha=0.05;
run;
```

The same model will be used for  $E_{max\_urge}(\text{uncontrolled})$  and  $E_{max\_plst}(\text{uncontrolled})$ , and all  $E_{max}$  of other questions in the Tobacco/Nicotine Withdrawal Questionnaire and Direct Effects of Product Questionnaire for the controlled and uncontrolled product uses in Part B. Baseline (pre-use) score will be included as a covariate for all pharmacodynamics measures for which a pre-use score is collected.

The analysis on  $E_{max\_urge(\text{controlled})}$  and  $E_{max\_plist(\text{controlled})}$  will be based on the pharmacodynamic and the completer populations separately.

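### Two primary endpoints, no multiplicity adjustment, and no statement of whether VLN must be lower than own-brand on one endpoint or on both

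*Protocol*

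**What the plan says.** Protocol 10.6.1 and SAP sections 4 and 9 name two primary endpoints, Emax_urge(controlled) and Emax_plst(controlled). The SAP adds that these two "will be the primary endpoints of the study while the remaining items will be secondary endpoints".

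For each endpoint, Protocol 12.4.3.2 states: "Comparisons will be made for Product A vs. B, A vs. C and B vs. C". Each contrast gets a difference, a p-value and a 95% CI. One contrast is given a role: "The comparison between Product A and Product C will be used as a comparison for internal validity".

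Protocol 12.4.3.6 reads in full: "Multiple comparison adjustments will not be made". The SAP has no multiplicity section, codes 0.05 on every estimate statement (for example "product 0 1 -1 /cl alpha=0.05"), and in section 12 declares no departures from the protocol, so the protocol's rule stands.

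The intended use is in Protocol 5.2: "Results of this study may provide supporting evidence for lower abuse liability of VLN cigarettes relative to own-brand cigarettes". The primary objective (Protocol 6.1, SAP section 2) covers abuse liability "under controlled use and uncontrolled use conditions", although both primary endpoints come from the controlled session only.

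**The concern.** The conclusion in Protocol 5.2 rests on A vs B, and two endpoints carry it equally. Nothing says how to read a split result, such as A significantly below B on pleasantness but not on urge reduction. That result could be called a success or a failure once the data are known. The study is open-label, with product codes open to staff and sponsor (Protocol 9.6), which makes a rule fixed in advance more valuable.

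If one endpoint is enough, the claim gets two chances at 0.05 and the error rate quoted per test is not the error rate of the claim.

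The objective adds a smaller ambiguity. It gives controlled and uncontrolled use the same standing, while the endpoint lists make every uncontrolled result secondary. The plan should say which results answer the primary question.

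**Working it through.** **The plan's own figure.** Protocol 12.2 opens each calculation with "Using a 2-sided Type I error rate at" 0.05 and treats the endpoints separately, for own-brand vs gum (B vs C) only. Read the stated SD as a per-period SD, so that the SD of a within-subject difference is √2 × SD, and use a paired t test:

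- Urge: difference 15.85, SD 28.44. √2 × 28.44 = 40.22. At n = 54 the noncentrality is 15.85 / (40.22/√54) = 2.90 and power is 81.1%. The smallest n for 80% is 53, against 54 stated.
- Pleasant: difference 35.21, SD 31.82. √2 × 31.82 = 45.00. At n = 16 the noncentrality is 35.21 / (45.00/√16) = 3.13 and power is 83.3%. The smallest n is 15, against 16 stated. At n = 54 power is 99.99%.

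Both stated sizes are reproduced to within one subject. Reading the SD as that of the paired difference gives 28 and 9, which does not match.

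**Error if either endpoint suffices.** Inputs: two endpoints, one contrast (A vs B), two-sided 0.05 each, A = B true on both.

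- Independent endpoints: 1 − (1 − 0.05)² = 0.0975.
- Bound for any correlation: 0.05 + 0.05 = 0.10.
- Lower direction only, independent: 1 − (1 − 0.025)² = 0.0494.
- Lower direction only, bound: 0.025 + 0.025 = 0.05.

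The documents give no correlation between the endpoints, so it is an assumption here. Simulation with 1,000,000 draws per value:

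| Assumed correlation | Either endpoint, two-sided | Either endpoint, A lower | Both endpoints, two-sided |
|---|---|---|---|
| 0 | 0.097 | 0.049 | 0.002 |
| 0.3 | 0.095 | 0.047 | 0.005 |
| 0.5 | 0.091 | 0.045 | 0.009 |
| 0.7 | 0.084 | 0.042 | 0.017 |
| 0.9 | 0.070 | 0.035 | 0.030 |

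At 0.8 the two-sided figure is 0.078. At a correlation of 1 there is no inflation.

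**Error if both are required.** A false claim needs every true null to be rejected, so its probability is at most that of rejecting one: 0.05 two-sided, or 0.025 in the lower direction. This holds whether one null or both are true, so no split of alpha is needed.

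**Power after the change, B vs C.** This is the only contrast with stated effects. At n = 54 the chance of significance on both endpoints is at least 0.8114 + 0.9999 − 1 = 0.8113, so about 81%, whatever the correlation. A Bonferroni split (0.025 per endpoint) would lower urge power to about 72%, and 63 to 64 completers would be needed to restore 80%.

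**The case against.** The case against has force on several points.

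*Nothing says that one endpoint suffices.* Protocol 12.2 sizes the endpoints separately and enrols for the larger number, which is compatible with requiring both. On that reading A vs B has no inflation. This stands, but compatibility is not a rule: the text fits either reading.

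*The claim is directional.* Half of the two-sided error consists of results with VLN above own-brand, which cannot support a claim of lower abuse liability. This stands. The false-lower rate doubles against its own nominal 0.025 but does not pass 0.05.

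*The plan is open about not adjusting, and this is a Phase I study whose results may only support a conclusion.* Also true. Every contrast has its own table, so a split would be visible. Visibility does not settle how it is to be read.

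Two stronger readings are tempting, and the documents do not support them.

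- A reader might count 13 items × 2 sessions × 3 contrasts = 78 model-based p-values and treat them as interchangeable. Protocol 10.6.2 and the SAP label everything beyond the two primary endpoints as secondary.
- A reader might count six primary tests and quote the error over all of them, 0.229 with independent endpoints. That needs all three products to be equal. Protocol 7.2 uses own-brand and gum as positive and negative controls, and 12.2 plans on differences of 15.85 and 35.21 points between them. If own-brand and gum differ on an endpoint, A = B and A = C cannot both hold there. At most one true null per endpoint remains, two in all, and the bound is again 2 × 0.05 = 0.10. The inflation comes from having two endpoints, not from the three contrasts.

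**Conclusion.** The gap is real and narrow. Two primary endpoints are tested without adjustment, and neither document says whether the claim that VLN is lower than own-brand needs one or both. If one suffices, the A vs B error is up to 0.10 two-sided (0.0975 if independent, about 0.095 to 0.08 for assumed correlations of 0.3 to 0.8), and a false lower finding goes from 0.025 to at most 0.05. If both are required there is no inflation. These figures assume that A equals B on both endpoints and, apart from the bounds, an endpoint correlation that the plan does not give.

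The data would remain valid either way. What is undefined is the interpretation of the main result, and a few sentences would settle it.

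**What to change.** In Protocol 12.4.3.6, repeated in SAP section 9, state that:

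1. The claim that VLN is lower than own-brand requires A below B at two-sided 0.05 on both Emax_urge(controlled) and Emax_plst(controlled), with no split of alpha.
2. B vs C is the sensitivity check of positive against negative control, and the comparison on which the sample size is based.
3. A vs C keeps its stated internal-validity role and is reported whatever A vs B shows.
4. All secondary Emax and PK p-values, including those from uncontrolled use, are nominal.
5. The primary claim rests on the controlled-use endpoints and uncontrolled use is supportive, so that objective and endpoints agree.

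The cost is wording in two documents. The planned 54 completers still give over 80% power for own-brand vs gum on each endpoint. There are two downsides. A win on one endpoint alone would no longer support the claim. Power for A vs B on both endpoints cannot be computed, because the plan states no A vs B effect, so the sponsor should state an assumed effect if it wants that figure.

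A separate correction is needed before the rule can be applied. The pharmacodynamic model code in SAP section 9 gives the A vs B estimate the coefficients 1 0 -1, the same as A vs C, whereas the PK code uses 1 -1 0.

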12.4.3.7. Tabulation of Individual Response Data

Individual subject pharmacodynamic data will be listed by measure and timepoint. A by-subject listing of derived pharmacodynamic endpoints (e.g., E_{max} , etc.) will also be provided.

12.4.4. Analysis of Pharmacokinetics

Refer to the SAP for details on analysis of PK.

Descriptive statistics of plasma nicotine concentrations will be tabulated by time point for each study product and product use condition. Derived PK parameters (both unadjusted and baseline

adjusted) will be summarized using descriptive statistics. Summaries will be provided for plasma nicotine-adjusted concentrations.

A linear mixed model for analysis of variance (Proc Mixed) will be performed on the baseline-adjusted log transformed nicotine PK parameters in Part B. The model will include sequence, study product, and period as fixed effects and subject nested-within sequence as a random effect. Sequence will be tested using subject nested-within sequence as the error term. From each model, the geometric LSM and 95% confidence intervals will be calculated for each study product. Separate analyses will be performed on the parameters calculated for the Controlled and Uncontrolled Use sessions. Geometric mean ratios for each pair comparison, 95% confidence interval and p value will be provided.

The same linear mixed effect model as used for the analysis of $C_{max(\text{controlled})}$ will be used for $C_{max(\text{uncontrolled})}$ of second product use in Part B, and for AUC following all product uses. The Hodges-Lehmann's method will be used to estimate the median differences and the 95% confidence interval of T_{max} and $T_{1/2}$ between the products.

12.4.5. Analysis of Safety Assessments

A by-subject AE data listing, including verbatim term, preferred term, study product, severity, and relationship to study product, will be provided. Study product use-emergent AEs will be summarized with tables. Frequencies of subjects with AEs, SAEs and incidence of those events, regardless of relationship to study product, will be summarized by study product and sorted by system organ class. Frequencies of AEs will be summarized by severity and relationship to study product. Clinical laboratory evaluations (serum chemistry, hematology, and urinalysis), vital signs measurements (blood pressure, pulse, respiration, and temperature) and ECG measurements (VR, PR, QRS, QT, and QTcF intervals) will be summarized descriptively. All concomitant medications recorded during the study will be listed by subject. Physical examinations will be listed by subject and time point of collection.

Details can be found in the SAP.

13. STUDY ADMINISTRATION AND INVESTIGATOR RESPONSIBILITIES

Additional details may be outlined in the Clinical Study Agreement (CSA) between the Sponsor and the investigational site.

13.1. Regulatory and Ethical Considerations

13.1.1. Ethical Conduct of the Study

An investigator will conduct the study in accordance with GCP and all applicable regulations, including, where applicable, the Declaration of Helsinki. The study will also be carried out in keeping with applicable national and local laws and regulations. This may include an inspection by the Sponsor's representatives and/or regulatory authority's representatives at any time.

13.1.2. Regulatory Authority and Ethics Approval

The investigational site's IRB must meet all relevant regulatory requirements. The study protocol and ICF will be reviewed by the IRB prior to enrolling subjects into the study; written approval from the committee must be received by the Sponsor before study product will be released to an investigator. An investigator is responsible for submitting all protocol or ICF changes and SAE reports to the IRB according to local procedures.

In accordance with applicable local regulatory requirements, an investigator may be obligated to provide periodic safety updates on the conduct of the study at his/her research site and notification of study closure to the IRB. Such periodic safety updates and notifications are the responsibility of an investigator and not of the Sponsor. The Sponsor will be provided with copies of all notifications sent to the IRB.

All relevant correspondence from the IRB will be forwarded by the respective study site to the Sponsor in a timely fashion.

